### **Electrocardiogram**

Twelve-lead triplicate ECGs will be collected at the time points specified in the **TIME AND EVENTS SCHEDULE** and when clinically indicated.

During the collection of ECGs, subjects should be in a quiet setting without distractions (eg, television, cell phones). Subjects should rest in a supine position for at least 5 minutes before ECG collection and should refrain from talking or moving arms or legs. If blood sampling or vital signs measurement is scheduled for the same time point as ECG recording, the procedures should preferably be performed in the following order: ECG(s), vital signs, blood draw.

At each time point at which triplicate ECGs are required, 3 individual ECG tracings should be obtained as closely as possible in succession, but no more than 2 minutes apart. The full set of triplicates should be completed in less than 10 minutes.

Evaluation of the triplicate 12-lead ECGs will be based on the mean value of the triplicate parameters.

Preferably, all ECGs (read centrally) will be read and interpreted under supervision of one and the same qualified person. Day 1, pre-dose ECG assessment will also be done locally on-site to determine eligibility.

Clinically relevant abnormalities occurring during the study should be recorded in the AE Section of the eCRF.

## **Vital Signs**

Blood pressure and pulse/heart rate measurements will be assessed with a completely automated device, if possible. All values will preferably be registered on a built-in recorder so that measurements are observer independent. Manual techniques will be used only if an automated device is not available.

Systolic and diastolic blood pressure and pulse rate (supine after at least 5 minutes rest) measured in a quiet setting without distractions (eg, television, cell phones) will be recorded.

Blood pressure and pulse/heart rate measurements should be preceded by at least 5 minutes of rest in a quiet setting without distractions (eg, television, cell phones).

Clinically relevant abnormalities (as defined in [Attachment 2](#)) occurring during the study should be recorded in the AE section of the eCRF.

## **Physical Examination**

A complete physical examination (including height, body weight, and body systems) will be performed at screening and early withdrawal. A symptom-directed physical examination (including body weight) will be performed at the time points indicated in the [TIME AND EVENTS SCHEDULE](#).

A complete physical examination includes the following: general appearance, eyes, ears, nose, throat, cardiovascular system, respiratory system, gastro-intestinal system, and skin and mucous membranes. A neurological and musculoskeletal examination will be performed, as well as an examination of the lymph nodes. Body weight and temperature will be measured. Height will be measured at the screening visit only. The skin examination includes an examination of the mucous membranes, but does not include a vaginal or rectal examination. However, if the subject develops a cutaneous reaction/rash, vaginal and rectal examinations may be done if clinically relevant. Additionally, a genito-urinary system examination may be done if deemed clinically relevant by the investigator.

At the other visits, a symptom-directed physical examination will be performed as indicated in the [TIME AND EVENTS SCHEDULE](#).

Any clinically relevant changes occurring during the study must be recorded in the AE Section of the eCRF.

## **Specific Toxicities**

For subjects reporting rash, acute systemic allergic reactions, AST/ALT elevations, renal complications, nausea and diarrhea, or other gastro-intestinal complaints, the following should be done.

***Rash***

For subjects reporting rash, please see [Attachment 3](#).

***Acute Systemic Allergic Reactions*****Grade 1 (Localized Urticaria [Wheals] With no Medical Intervention Indicated)**

Subjects may continue the intake of study drugs.

Cetirizine, levocetirizine, topical corticosteroids or antipruritic agents may be prescribed.

Subjects should be advised to contact the investigator immediately if there is any worsening of the acute systemic allergic reaction.

**Grade 2 (Localized Urticaria With Medical Intervention Indicated, or Mild Angioedema With no Medical Intervention Indicated)**

Subjects may continue the intake of study drugs.

Cetirizine, levocetirizine, topical corticosteroids or antipruritic agents may be prescribed.

Subjects should be advised to contact the investigator immediately if there is any worsening of the acute systemic allergic reaction, in which case the subject will permanently discontinue the intake of JNJ-56136379. Rechallenge is not allowed. The subject's NA treatment may be discontinued based on investigator judgement in consultation with the sponsor.

**Grade 3 (Generalized Urticaria, Angioedema With Medical Intervention Indicated, or Symptomatic Mild Bronchospasm) and Grade 4 (Acute Anaphylaxis, Life-Threatening Bronchospasm, or Laryngeal Edema)**

Subjects will permanently discontinue the intake of JNJ-56136379. Rechallenge is not allowed. The subject's NA treatment may be discontinued based on investigator judgement in consultation with the sponsor.

Subjects will be treated as clinically appropriate. Subjects should be followed until resolution of the AE and standard management should be undertaken.

***AST and ALT Elevation*****Grade 1 ( $\geq 1.25$  to  $<2.50 \times$  ULN), or Grade 2 ( $\geq 2.50$  to  $<5.00 \times$  ULN)**

Subjects may continue the intake of study drugs.

Subjects should be followed until resolution (return to baseline) or stabilization of AST/ALT elevation (to be agreed upon with the sponsor).

**Grade 3 ( $\geq 5.00$  to  $< 10.00 \times$  ULN), or Grade 4 ( $\geq 10.00 \times$  ULN)**

The investigator should contact the sponsor to discuss the case when:

- the ALT and/or AST elevations during treatment are  $\geq 2$  times the value at baseline, OR
- the ALT and/or AST values increase by  $\geq 2$  grades compared to the grade at baseline.
- the ALT and/or AST values increase to grade 4, regardless of the baseline value or grade.

Subjects should be followed until resolution (return to baseline) or stabilization of AST/ALT elevation.

***Renal Complications***

If renal complications develop, subjects should be closely monitored for disturbances in serum creatinine and for abnormalities in urine analysis (eg, proteinuria). Additional investigations can be performed at the investigator's discretion. Subjects must be treated as clinically appropriate.

Subjects who develop **grade 1** or **2** abnormalities in **serum creatinine** or **urinalysis** may continue the intake of study drugs (unless they develop abnormalities in serum creatinine or urinalysis considered at least possibly related to the study drugs by the investigator) or be withdrawn from further study treatment based on the investigator's clinical judgment.

Subjects who develop confirmed **grade 3** or **4** abnormalities in **serum creatinine** will permanently discontinue the intake of JNJ-56136379 regardless of the relationship to the study drugs. The subject may continue ETV or switch from TDF to ETV at the investigator's discretion.

Subjects who are receiving TDF and develop confirmed treatment-emergent **grade 3** or **4** abnormalities in **urinalysis**, considered at least possibly related to TDF, may switch to ETV and continue JNJ-56136379 for 4-8 weeks. If the urinalysis abnormality persists at the end of the 4-8 weeks NA switching phase, JNJ-56136379 must be discontinued. Subjects may continue NA treatment at the investigator's discretion and enter follow-up. Subjects on TDF or ETV treatment will be able to continue study treatment (JNJ-56136379 + TDF or ETV), without the need for treatment modification, if the **urinalysis** abnormality can be attributed to any other concomitant disease and its medication (eg, diabetes mellitus).

If the confirmed **grade 3** or **4** **urinalysis** abnormality is not considered at least possibly related to TDF or ETV, or any other concomitant disease and its medication, JNJ-56136379 must be discontinued. Subjects may continue NA treatment at the investigator's discretion and enter follow-up. For further details on study treatment discontinuation, refer to Section 10.2.

All subjects who develop confirmed **grade 3** or **4** abnormalities in **serum creatinine** or **urinalysis** should be followed appropriately until resolution of AE or toxicity. Rechallenge of JNJ-56136379 is not allowed in subjects who need to discontinue treatment with JNJ-56136379.

The grades are based on the DAIDS Toxicity Grading Scale.

### ***Nausea (With or Without Vomiting)***

#### **Grade 1 (Transient [<24 Hours] or Intermittent Nausea With no or Minimal Interference With Oral Intake)**

Subjects may continue the intake of study drugs and may be treated as needed with anti-emetics given orally or rectally.

#### **Grade 2 (Persistent Nausea Resulting in Decreased Oral Intake for 24 to 48 Hours)**

Subjects may be treated as needed with anti-emetics given orally or rectally. If the nausea persists despite anti-emetics or increases in severity, subjects will permanently discontinue the intake of JNJ-56136379. The subject's NA treatment may be discontinued based on investigator judgement in consultation with the sponsor.

#### **Grade 3 (Persistent Nausea Resulting in Minimal Oral Intake for >48 Hours, or Rehydration Indicated) and Grade 4 (Life-Threatening Consequences)**

Subjects will permanently discontinue the intake of JNJ-56136379. Rechallenge is not allowed. The subject's NA treatment may be discontinued based on investigator judgement in consultation with the sponsor.

### ***Diarrhea***

#### **Grade 1 (Transient or Intermittent Episodes of Unformed Stools, or Increase of $\leq 3$ Stools Over Baseline per 24-Hour Period)**

Subjects may continue the intake of study drugs. Loperamide can be administered.

#### **Grade 2 (Persistent Episodes of Unformed to Watery Stools, or Increase of 4 to 6 Stools Over Baseline per 24-Hour Period)**

Subjects may continue the intake of study drugs. Loperamide can be administered.

#### **Grade 3 (Increase of $\geq 7$ Stools per 24-Hour Period, or Intravenous Fluid Replacement Indicated) or Grade 4 (Life-Threatening Consequences)**

Subjects will permanently discontinue the intake of JNJ-56136379. Subjects should be followed until resolution of the AE. Rechallenge is not allowed. The subject's NA treatment may be discontinued based on investigator judgement in consultation with the sponsor.

### **9.10. Sample Collection and Handling**

The actual dates and times of sample collection must be recorded in the eCRF or laboratory requisition form.

Refer to the **TIME AND EVENTS SCHEDULE** for the timing and frequency of all sample collections.

Instructions for the collection, handling, storage, and shipment of samples are found in the laboratory manual that will be provided. Collection, handling, storage, and shipment of samples must be under the specified, and where applicable, controlled temperature conditions as indicated in the laboratory manual.

## **10. SUBJECT COMPLETION/DISCONTINUATION OF STUDY TREATMENT/ WITHDRAWAL FROM THE STUDY**

### **10.1. Completion**

For subjects who are not eligible to participate in the treatment extension phase:

- Subjects will be considered to have completed the study treatment if they have completed 24 weeks of study drug administration, after which they will discontinue JNJ-56136379 or placebo treatment. NA treatment (either ETV or TDF as per local practice) should be started (in case of JNJ-56136379 monotherapy, ie, Treatment Arms 1 and 6) or continued (in case NA treatment was part of the assigned study treatment, ie, Treatment Arms 2 to 5 and 7 to 10) as per local treatment guidelines.
- Subjects will be considered to have completed the study if they have completed the assessments of the end of study visit (Follow-up [FU] Week 24 [Schedule 1]).
- For subjects who do not continue or start NA treatment at Week 24, an additional 24-week follow-up (as per local treatment guidelines) by their primary care physician, outside of the study, is recommended after study completion.

For subjects who continue treatment in the extension phase:

- Subjects will be considered to have completed the study treatment if they have completed 48 weeks of study drug administration, after which they will discontinue JNJ-56136379 or placebo treatment. At Week 48:
  - o Subjects who meet all of the Individual Subject Treatment Completion Criteria (see Section 6.3) will complete all treatment. These subjects will be followed-up until 48 weeks after EOT (Schedule 2). If, during the 48-week follow-up, a subject meets one of the re-treatment criteria described in Section 6.4, NA treatment (ETV or TDF) should be re-started.
  - o Subjects who do not meet the Individual Subject Treatment Completion Criteria should start (in case of JNJ-56136379 monotherapy, ie, Treatment Arms 1 and 6) or continue (in case NA treatment was part of the assigned study treatment, ie, Treatment Arms 2 to 5 and 7 to 10) NA treatment as per local treatment guidelines. These subjects will be followed-up until 24 weeks after the end of study treatment (Schedule 1).
- Subjects will be considered to have completed the study if they have completed the assessments of the end of study visit (FU Week 24 [Schedule 1] or FU Week 48 [Schedule 2]).

- For subjects who do not meet the Individual Subject Treatment Completion Criteria and do not start or continue NA treatment at Week 48, an additional 24-week follow-up (as per local treatment guidelines) by their primary care physician, outside of the study, is recommended after study completion.

The study is considered completed with the last visit of the last subject participating in the study.

## **10.2. Discontinuation of Study Treatment/Withdrawal from the Study**

### **Discontinuation of Study Treatment**

A subject will not be automatically withdrawn from the study if he or she has to discontinue study treatment before the end of the 24- or 48 week treatment phase, as applicable.

A subject's JNJ-56136379 treatment must be discontinued and NA may be discontinued based on investigator judgement in consultation with the sponsor if:

1. The subject withdraws consent.
2. The investigator believes that for safety reasons or tolerability reasons (eg, AE) it is in the best interest of the subject to discontinue study treatment.
3. The subject becomes pregnant.
4. The subject has a  $\geq$  gradea 3 rash (see [Attachment 3](#)).
5. The subject has a  $\geq$  grade 3 allergic reaction, nausea, or diarrhea.
6. The subject has a grade 4 AE or confirmed laboratory abnormality (with the exception of ALT/AST elevations) considered at least possibly related to study drugs by the investigator.
7. The subject experiences a treatment-emergent elevation of ALT  $>2x$  baseline value, in combination with either direct bilirubin  $>1.2x$  ULN or INR  $>1.5x$  ULN or serum albumin  $<$  LLN, confirmed by retesting.
8. The subject has signs of hepatic decompensation (ie, clinical evidence of ascites, bleeding varices, or hepatic encephalopathy).
9. The subject has a confirmed  $\geq$  grade 3 serum creatinine abnormality, regardless of the relationship to the study drugs. In this case, JNJ-56136379 must be discontinued. The subject may continue ETV or switch from TDF to ETV at the investigator's discretion and enter follow-up.

Subjects who are receiving TDF and develop confirmed treatment-emergent  $\geq$  grade 3 abnormalities in urinalysis, considered at least possibly related to TDF, may switch to ETV and continue JNJ-56136379 for 4-8 weeks. If the urinalysis abnormality persists at the end of the 4-8 weeks NA switching phase, JNJ-56136379 must be discontinued. Subjects may continue NA treatment at the investigator's discretion and enter follow-up.

---

a Grades in this list are per the DAIDS Toxicity Grading Scale.

If the confirmed  $\geq$  grade 3 urinalysis abnormality is not considered at least possibly related to TDF or ETV, or any other concomitant disease and its medication, JNJ-56136379 must be discontinued. Subjects may continue NA treatment at the investigator's discretion and enter follow-up.

10. The subject has a QTcF prolongation (defined as a QTcF value of  $>500$  ms, or an increase from baseline of  $>60$  ms) at any given time point (confirmed by repeat ECG).
11. The subject has at Week 4  $<1 \log_{10}$  IU/mL decline in HBV DNA from baseline, confirmed by retesting at the Week 8 visit (treatment-naïve only).
12. The subject has confirmed HBV virological breakthrough (ie, confirmed on-treatment HBV DNA increase by  $>1 \log_{10}$  IU/mL from nadir level or confirmed on-treatment HBV DNA level  $>200$  IU/mL in subjects who had HBV DNA level  $<$  LLOQ of the HBV DNA assay).
13. The subject requires treatment with any of the disallowed medications listed in Section 8.

Retesting for confirmation of the above-mentioned abnormal safety parameters (ie, not applicable to criteria 11 and 12 listed above) should take place within 72 hours after the initial results become available and may require an unscheduled visit.

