### **Clinical Laboratory Tests**

Blood samples for serum chemistry and hematology and a urine sample for urinalysis will be collected. The investigator must review the laboratory results, document this review, and record any clinically relevant changes occurring during the study in the AE section of the eCRF. The laboratory reports must be filed with the source documents.

Subjects need to have fasted for at least 10 hours before biochemistry samples are taken for measurement of phosphorus, calcium, creatinine clearance, and lipids. Subjects should bring their study drug with them to each visit and have that day's intake at the site.

In case a grade 3 or grade 4 laboratory abnormality occurs, a confirmatory test must be performed preferably within 48 hours but no later than 72 hours after the results have become available.

The following tests will be performed by the selected laboratory:

- Hematology Panel
 

-hemoglobin	-WBC differential (including %)
-hematocrit	*neutrophils
-red blood cell (RBC) count	*lymphocytes
-RBC parameters	*monocytes
*mean corpuscular hemoglobin (MCH)	*eosinophils
*MCH concentration	*basophils
*mean corpuscular volume	-platelet count
-white blood cell (WBC) count with differential	

A WBC evaluation may include any abnormal cells, which will then be reported by the laboratory. A RBC evaluation may include abnormalities in the RBC count, RBC parameters, or RBC morphology, which will then be reported by the laboratory. In addition, any other abnormal cells in a blood smear will also be reported.

- Serum Chemistry Panel
 

-sodium	-calcium
-potassium	-phosphate
-chloride	-albumin
-bicarbonate	-total protein
-blood urea nitrogen	-total cholesterol
-creatinine	-high-density lipoprotein cholesterol
-glucose	-low-density lipoprotein cholesterol
-AST	-triglycerides
-ALT	-magnesium
-gamma-glutamyltransferase	- $\alpha_1$ -acid glycoprotein
-total, conjugated and unconjugated bilirubin	-calculated creatinine clearance (by MDRD formula)
-alkaline phosphatase	-lipase
-creatine phosphokinase	-amylase (reflex testing of pancreatic amylase should be done in case of post-screening amylase or lipase increase)
-lactic acid dehydrogenase	-fibrinogen (on blood)
-uric acid	-C-reactive protein

- Urinalysis

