A urine sample must be provided for urinalysis. Specific gravity, pH, glucose, protein, blood, ketones, bilirubin, urobilinogen, nitrite, and leukocyte esterase will be determined using dipstick. In case of positive dipstick results, the sediment will be examined microscopically for RBCs, WBCs, and epithelial cells and an additional examination will be performed on the positive urinary parameter (eg, quantification as applicable). Crystals, casts and bacteria will only be reported if they are present.

- At screening, a serum pregnancy test will be performed for women of childbearing potential.
- At screening, an FSH test will be performed for postmenopausal women.

- At time points as indicated in the **TIME AND EVENTS SCHEDULE**, a urine pregnancy test will be performed (women of childbearing potential only).
- At screening, a HIV-1 and -2 test, and hepatitis A, B, C, D, and E tests will be performed.
- At screening and time points as indicated in the **TIME AND EVENTS SCHEDULE**, tests will be performed for HBsAg, HBeAg, HBcAg, and anti-HBs and anti-HBe antibodies.
- At screening and time points as indicated in the **TIME AND EVENTS SCHEDULE**, determination of coagulation parameters will be performed. INR will be calculated by the central laboratory.
- At screening, alpha-fetoprotein will be measured.

In case of **rash**, blood samples (mandatory blood sample for safety in case of Grade 3 or Grade 4 rash and at the discretion of the investigator in case of Grade 1 or Grade 2 rash) need to be taken for safety laboratory testing, and are to be processed by the local laboratory. These samples need to be taken at unscheduled visits as described in [Attachment 3](#). The following parameters need to be tested: AST, ALT, erythrocyte sedimentation rate, creatinine, and a complete blood cell count (including hemoglobin, hematocrit, RBC count, WBC count, neutrophils, lymphocytes, monocytes, eosinophils, basophils, and platelet count).

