### 12.1.3. Severity Criteria

An assessment of severity grade will be made by the investigator using the general categorical descriptors outlined in the DAIDS Toxicity Grading Scale.

The investigator should use clinical judgment in assessing the severity of events not directly experienced by the subject (eg, laboratory abnormalities).

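### For a confirmed grade 4 urinalysis abnormality possibly related to TDF, Section 10.2 criterion 6 requires JNJ-56136379 to stop while criterion 9 and Section 9.9 permit 4-8 more weeks, with no precedence stated

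*Protocol*

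**What the plan says.** The list of stopping criteria in Protocol Section 10.2 opens with a mandatory consequence for the investigational drug: "JNJ-56136379 treatment must be discontinued and NA may be discontinued based on investigator judgement in consultation with the sponsor if" any listed criterion is met. Criterion 6 names a "grade 4 AE or confirmed laboratory abnormality (with the exception of ALT/AST elevations) considered at least possibly related to study drugs". Its only carve-out is ALT/AST.

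Criterion 9 deals with the kidney. Its urinalysis paragraph covers subjects on TDF with a confirmed treatment-emergent abnormality of grade 3 or higher which, if "considered at least possibly related to TDF, may switch to ETV and continue JNJ-56136379 for 4-8 weeks". JNJ-56136379 must then stop if the abnormality is still present at the end of that window. Section 9.9 (Renal Complications) repeats the permission and names grades 3 and 4 explicitly. It refers the reader to Section 10.2 for further detail but sets no order between the rules.

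Two further provisions fix the timing and weight of the decision. Retesting of abnormal safety parameters "should take place within 72 hours after the initial results become available" (Section 10.2), and Section 9.9 adds that "Rechallenge of JNJ-56136379 is not allowed in subjects who need to discontinue treatment with JNJ-56136379".

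**The concern.** This is a safety stopping rule, and for one type of case it gives a site two different written actions. A site that works from the renal text alone will keep dosing a subject for whom criterion 6, three items earlier in the same list, makes stopping compulsory. A site that works from criterion 6 will withdraw the drug for good from a subject whom the renal text would have allowed to continue. The choice has to be made soon after the confirmatory test, and a stop cannot be undone. Two sites could therefore handle identical cases differently, and one of them would be in breach of the protocol while following its text.

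**Working it through.** The plan gives no figure to reproduce here. The check is a comparison of rules, followed by short arithmetic on dosing.

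**Does criterion 6 reach a TDF-related urinalysis result?** It needs three things.

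- Study drugs must include TDF. Section 6 defines them as JNJ-56136379, NA and placebo, so they do.
- Urinalysis must count as laboratory testing. Section 9.9 lists it among the clinical laboratory tests.
- No exemption may apply. Only ALT/AST is exempt.

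**The rules side by side, for a subject on JNJ-56136379 plus TDF:**

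| Confirmed treatment-emergent finding | Criterion 6 | Criterion 9 and Section 9.9 | Conflict? |
|---|---|---|---|
| Grade 3 urinalysis, possibly TDF-related | not triggered (grade 4 only) | may switch to ETV and continue 4-8 weeks | no |
| **Grade 4 urinalysis, possibly TDF-related** | **must stop** | **may switch to ETV and continue 4-8 weeks** | **yes** |
| Grade 3 or 4 urinalysis, not attributed to the NA or to a concomitant disease | stop at grade 4 if possibly related to study drugs | must stop | no |
| Grade 3 or 4 serum creatinine | stop at grade 4 if possibly related to study drugs | must stop, whatever the relationship | no |

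The overlap is the second row only.

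**Size per affected subject.** Dosing is once daily. The longest switch window is 8 weeks × 7 = 56 doses. That is 56 × 75 mg = 4,200 mg in Part A or 56 × 250 mg = 14,000 mg in Part B. It is 56/168 = 33% of a 24-week course, or 56/336 = 17% of a 48-week course. The lower end of the window, 4 × 7 = 28 doses, is not a floor. An event at Week 22 in a subject who does not enter the extension leaves 2 × 7 = 14 doses, and criterion 2 lets the investigator stop at any time. On placebo + NA the extra exposure to JNJ-56136379 is zero. Those arms are planned at 10 + 10 = 20 of the 10 + 30 + 10 + 30 = 80 subjects assigned an NA from Day 1 in each part (Section 3.1).

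**Can a grade 4 urinalysis result occur?** Section 9.9 lists the tests: "Specific gravity, pH, glucose, protein, blood, ketones, bilirubin, urobilinogen, nitrite, and leukocyte esterase will be determined using dipstick". That is 10 items. SAP Table 6 assigns DAIDS grades to 2 of them, protein and glucose, and SAP Table 7 ends at grade 3 for both. Table 6 has no row for urine blood, so it is silent on that item. Table 7 governs the analysis and not site decisions. Sites grade on the DAIDS scale (Section 10.2, footnote a), which is not reproduced, and Section 12.1.3 adds: "The investigator should use clinical judgment in assessing the severity of events not directly experienced by the subject (eg, laboratory abnormalities)". Section 9.9 itself writes rules for grade 4 urinalysis, so the protocol contemplates it. Nothing in the documents shows that a case will arise.

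**The case against.** The strongest reply is that ordinary reading settles the matter. Criterion 6 is a catch-all. The urinalysis paragraph covers one test and one suspected drug, with a defined switch, a reassessment and a stop if the finding persists. Section 9.9 names grade 4, so the drafters considered it. The switch is optional, and criterion 2 lets the investigator stop whenever safety calls for it. On this view all that is missing is a short cross-reference.

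Part of this stands. The two rules are not incompatible orders, since stopping satisfies both, and naming grade 4 in Section 9.9 is some evidence that continuation was intended. But the protocol nowhere says that the specific rule overrides the general one, and criterion 6 carries an explicit exemption for ALT/AST and none for urinalysis. A site using the written permission still breaches a mandatory stop in the same list.

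The objection also stands against stronger readings that a reader might infer:

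- *Subjects will be dosed when they should have stopped.* The only reproduced urinalysis grading ends at grade 3, so there may be no such case.
- *Every affected subject gets at least 28 further doses.* The Week 22 example shows otherwise.
- *The sponsor meant stopping to prevail.* The text does not settle which branch was intended.
- *Grade 1-2 urinalysis is also inconsistent, because Section 9.9 offers no switch there.* No Section 10.2 criterion requires a stop specifically for a grade 1-2 urinalysis result, and Section 9.9 leaves such cases to clinical judgment. That is not a conflict, and adding a switch would be a new clinical rule.

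**Conclusion.** The concern holds, and it is minor. For one case, a confirmed treatment-emergent grade 4 urinalysis abnormality at least possibly related to TDF, a mandatory stop and a written permission to continue overlap without precedence. This rests on reading grade 4 in criterion 6 as applying to laboratory abnormalities as well as to AEs, which is the narrower reading, and on the Section 6 definition of study drugs.

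The consequence is up to 56 further once-daily doses over the switch window per affected subject on active drug, fewer if treatment ends sooner or the investigator stops under criterion 2, and none on placebo. The number of affected subjects is small and may be zero. Confidence is high for the overlap in the text and low for whether it will ever be exercised. No efficacy figure, power or sample size depends on it.

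**What to change.** Make the two rules agree; the sponsor should choose the branch.

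- **Conservative default.** In the TDF-to-ETV switch sentence, restrict the grade to 3 in both Section 9.9 and criterion 9. Add one sentence saying that a confirmed grade 4 urinalysis abnormality at least possibly related to study drugs is handled under criterion 6. Leave the sentence on abnormalities not attributed to the NA or a concomitant disease at grade 3 or higher. The downside is irreversible loss of JNJ-56136379 in the few, if any, grade 4 cases.
- **If continuation at grade 4 is intended.** Leave the renal text alone and extend the exception in criterion 6 beyond ALT/AST with the words *and urinalysis abnormalities managed under criterion 9*.

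The first option costs one phrase in each of two sections plus one cross-reference sentence; the second costs one phrase. Either can go in the next amendment with a memo to sites, and neither adds an assessment.
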